For WP2, data on volume will be linked to responses to our national survey of governance leads in NHS and independent hospitals. For WP3 we will provide information on potential clusters of NHS and independent hospitals to inform case study selection. For WP4 and WP5 we will provide information on volume, case-mix and coding practice for areas of overlap across the NHS and independent sector. This list is likely to include procedures in specialties such as general surgery, urology, trauma and orthopaedics, ENT, ophthalmology and cardiology.

Case-mix

Using patient level data from Hospital Episode Statistics we will compare the case-mix of patients. This will include patients whose treatment is NHS funded regardless of where the treatment occurs, and privately funded care in NHS private patient units. We will compare patient socio-demographic characteristics (gender, age, ethnicity, deprivation of the patient's local area) and medical characteristics (length of stay, presence and count of comorbidities). These case-mix variables will be summarised by provider type (NHS hospital, NHS private patient unit), funding source, geographical region and over time.

For our analysis of case-mix we will estimate a prediction model for patients in quadrants A, B and C using mortality as the outcome for each patient. We will compare expected vs actual outcomes for patients in each quadrant after performing adjustment for casemix variables and provider characteristics. We will summarise the mean risk ratios for patients in each quadrant to identify

differences that may arise due to differences in casemix. We will repeat the analyses for the clinical specialties with the highest volumes across the three quadrants. Findings from this analysis will inform WP4 and WP5.

Coding practice

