Indicator 6 uses patient-reported outcome measures (PROMs) data that are routinely collected in both NHS and independent hospitals for two surgical procedures: planned hip and knee replacement surgery (see section on datasets above). We will request NHS Digital to supply us with data from the national PROMs programme, which covers NHS-funded care only, linked to a corresponding Hospital Episode Statistics extract.

We will conduct separate multivariate regression analysis of the six indicators stratified by type of procedure. All regression models will include a set of indicator variables denoting the three quadrants, and the associated regression coefficients will be used to test for differences in quality and safety across hospital types and funding sources. All regression models will control for known confounders such as patient demographic characteristics (i.e. sex, age, ethnicity, area-level deprivation based on the index of multiple deprivation score for the patient's lower-layer super output area (LSOA) of residence), diagnosis, comorbidities, past healthcare utilisation as captured in Hospital Episode Statistics, and admission information (e.g. calendar month of admission). In specifying the case-mix adjustment we will draw on previous work [40, 41, 42] and insights from the data quality assessment conducted in WP1.

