It is well known that administrative hospital data do not capture all patient factors that determine outcomes. If unobserved confounders are not equally distributed across admissions in the four quadrants, for example because patients with certain unobserved characteristics are more likely to self-fund their care or be treated in independent hospitals, then this may bias comparative assessments. To explore the impact of unobserved confounding, we will build on our previous work [22, 43, 44] and specify instrumental variable (IV) regression models in which the observed choice of funding source and hospital type (i.e. *selection into treatment* in causal inference terminology) for each admission is modelled as a function of exogenous variation in i) difference in the travel distances to the nearest NHS and independent hospital (as a proxy for ease of access), and ii) median house prices in the patient's LSOA of residence (as a proxy for relative wealth and, thus, affordability of private care). Under the assumptions that these two instrumental variables are not directly correlated with outcome of care (other than through the observed choice of funding source / hospital type) and are strong determinants of the observed choice, this IV approach permits achieving quasi-randomisation in observational data.

Using the result from our analysis we will calculate hospital-level reports for our case-study sites by means of indirect standardisation. For each hospital and indicator, we will calculate the case-mix adjusted outcome (e.g. the rate of unplanned readmissions following planned hip replacement surgery) and plot these using funnel plots; a presentational format of performance assessments that clinicians and managers are increasingly familiar with. We will explore the utility of these data for clinical governance through our case study site fieldwork in WP3.

Qualitative focus groups/interviews with patients and carers to explore quality and safety

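### WP1 adjusts expected mortality for case-mix and provider characteristics, then reads the ratios by quadrant as case-mix differences, which they cannot show; WP5's hospital reports need a stated source for expected counts

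*Protocol*

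**What the plan says.** **WP1, Case-mix (Protocol).** The team states that "we will estimate a prediction model for patients in quadrants A, B and C using mortality as the outcome for each patient". It continues: "We will compare expected vs actual outcomes for patients in each quadrant after performing adjustment for casemix variables and provider characteristics". The next sentence begins "We will summarise the mean risk ratios for patients in each quadrant to identify" and ends by naming its target as "differences that may arise due to differences in casemix". The provider characteristics are not listed, and the term mean risk ratio is not defined. The findings are to feed WP4 and WP5.

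**WP5, Quantitative analysis of hospital data (Protocol).** Each index admission is assigned to quadrant A, B or C by funding source and hospital type. On the models: "All regression models will include a set of indicator variables denoting the three quadrants". The sector comparison is then made on those terms: "the associated regression coefficients will be used to test for differences in quality and safety across hospital types and funding sources". On the reports for case-study sites: "Using the result from our analysis we will calculate hospital-level reports for our case-study sites by means of indirect standardisation". The quantity reported is described thus: "For each hospital and indicator, we will calculate the case-mix adjusted outcome". The section does not say whether the quadrant term is kept, dropped or set to a reference when expected values are computed.

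**The concern.** There are two faults in WP1 and a related gap in WP5.

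1. **The WP1 measure does not match its stated purpose.** Dividing actual by case-mix-adjusted expected mortality removes case-mix. What remains is everything else: quality, unmeasured severity, coding. Case-mix differences between quadrants would show in the expected risk itself. Read as the protocol proposes, a residual difference would be reported as a case-mix difference and carried into WP4 and WP5.

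2. **Provider characteristics overlap with the grouping being compared.** Hospital type is one of the two axes that define a quadrant. Any provider variable that encodes it removes part or all of the quadrant contrast from the expected values.

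3. **WP5 hospital reports.** If fitted values from models with quadrant indicators serve as expected counts, each hospital is benchmarked only against its own quadrant. The case-study clusters deliberately mix NHS and independent hospitals, so readers could see both sectors centred on the same line and infer a parity that the model imposed.

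**Working it through.** The protocol gives no figure to reproduce here. The check is algebra first, then a simulation for size.

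**Algebra.** Take a logistic model fitted by maximum likelihood, with logit(p) = a + b·x + g_B·B + g_C·C, where x is case-mix and B and C are quadrant indicators. The score equation for g_C is Σ over C of (y − p) = 0, so O_C = E_C and O/E = 1. The same holds for B and, through the intercept, for A. Least squares gives the same identity for continuous outcomes. With an ownership indicator only (independent against NHS), O/E = 1 in C and in A and B combined, but not in B alone. A characteristic merely correlated with sector has no such identity.

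A corollary: with quadrant-type indicators in the model, the mean predicted risk in a quadrant equals its crude mortality. That model's predicted risk then cannot isolate case-mix either.

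**Simulation inputs.**
- From Diagram 1 of the protocol: shares A 88%, B 0.6%, C 4.6%. The total is 93.2, so the weights are 88/93.2 = 0.9442, 0.6/93.2 = 0.0064 and 4.6/93.2 = 0.0494.
- Assumed, not in the documents: 600,000 admissions; baseline event rate 5% or 1%; odds ratio for C of 0.7 or 1.4, and for B of 0.8 or 1.2; one case-mix score (log odds ratio 0.6 per unit), lower on average by 0.5 in C and 0.3 in B; 150 NHS and 150 independent hospitals with a between-hospital SD of 0.15 on the log-odds scale; a volume-like characteristic averaging 1.5 SD higher in NHS hospitals.

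**O/E for quadrant C, by what enters the expected value.**

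| Expected value from | 5%, OR 0.7 | 5%, OR 1.4 | 1%, OR 0.7 |
|---|---|---|---|
| True quadrant-A risk (benchmark) | 0.693 | 1.343 | 0.644 |
| Case-mix only | 0.712 | 1.317 | 0.666 |
| Case-mix + correlated characteristic | 0.738 | 1.252 | 0.658 |
| Case-mix + ownership | 1.000 | 1.000 | 1.000 |
| Case-mix + quadrant | 1.000 | 1.000 | 1.000 |
| Same model, quadrant terms set to A | 0.701 | 1.340 | 0.655 |

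The correlated characteristic moved the ratio by 0.026 and 0.065 towards 1 in the first two scenarios, and by 0.008 away from 1 in the third. With ownership in the model, B stayed at 0.733, 1.253 and 0.869.

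**WP5 hospital reports.** With expected counts from the quadrant-adjusted fitted values, mean hospital O/E was 1.000 for NHS hospitals in all three scenarios, and 1.001, 0.999 and 1.009 for independent hospitals. With the quadrant terms set to A, the independent means were 0.702, 1.339 and 0.661, and the NHS means 0.998, 1.001 and 0.999. Spread between hospitals within a sector survives either way (NHS SD about 0.15 at the 5% rate with own-quadrant expected values).

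**WP5 sector test.** The fitted C coefficient at the 5% rate was −0.374 and +0.315, against true values ln 0.7 = −0.357 and ln 1.4 = +0.336. It recovers the effect.

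**The case against.** A reader might infer that the plan hides sector differences by construction: that WP1's ratios must all equal 1, and that WP5's funnel plots cannot show one sector doing worse. The documents do not support that reading.

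- WP1 does not name its provider characteristics. Provider type appears in that section as a variable for summarising case-mix, not as a model term. Exact masking needs provider type, ownership or quadrant in the model.
- WP5 does not say that expected counts keep the quadrant term. It calls the output case-mix adjusted, which can fairly be read as patient factors only, and the handling of that term could be settled in an analysis plan that is not shown.
- The protocol does not ask the hospital reports to show sector differences. Those are tested on the quadrant coefficients, and the reports serve governance at the case-study sites.

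All three points stand, and they limit the WP5 part to a conditional risk. The case-mix label does not fully remove that risk, because the protocol uses it loosely: WP1 lists length of stay among its case-mix variables, while WP5 treats it as an outcome.

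It can also be said that mean risk ratio is undefined and might mean relative predicted risk rather than observed over expected. That would suit the stated purpose better. But predicted risk from a model with provider characteristics mixes patient and provider effects, so it still would not isolate case-mix. The mismatch in WP1 therefore stands on either reading.

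**Conclusion.** The point holds for WP1 as written. Ratios already adjusted for case-mix cannot identify case-mix differences, and that does not depend on which provider characteristics are chosen. How much these also absorb the quadrant contrast does depend on the choice: completely (O/E = 1) for any category whose indicator is in the model, and partly or negligibly for characteristics only correlated with sector.

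The identity assumes unpenalised maximum likelihood or least squares, with expected values taken from the data used for fitting. It does not depend on the simulated rates or odds ratios. The other sizes do, and they illustrate rather than predict.

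For WP5 the conclusion is conditional: if fitted values become expected counts, hospitals are compared only within their own quadrant. The WP5 tests of sector differences on the quadrant coefficients are not affected.

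**What to change.** **WP1.** Fit the mortality model on patient variables only. Report mean predicted risk by quadrant as the case-mix difference, and observed/expected by quadrant as the residual difference, and define the ratio. If provider characteristics are of interest, list them and add them in a separate, labelled secondary model.

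**WP5.** Keep the quadrant indicators for the hypothesis tests. For indirect standardisation, state that expected counts come from patient terms only, or from the existing model with the quadrant term set to one common reference for every hospital. In the simulation both routes kept the sector difference visible (C: 0.71 and 0.70 against a benchmark of 0.69; 1.32 and 1.34 against 1.34; 0.67 and 0.66 against 0.64).

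**Cost.** A few sentences in the protocol, a refit of the WP1 model and one prediction step in WP5. No new data are needed.

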The overall aim of this research is to provide evidence on the quality and safety of patient care in NHS and independent hospitals and the effectiveness and impact of shared arrangements for clinical governance. There are longstanding concerns among policymakers and leaders in both the NHS and independent healthcare sectors, and reports such as the Paterson inquiry [3], the medicines and medical devices safety review [5], a recent Healthcare Safety Investigation Board report [6] and the Care Quality Commission state of care report [7]) have highlighted the need for improvement.

Empirical evidence on the quality and safety of care has been limited by the lack of comparable routine data across both NHS and independent hospitals, but that is now changing with reforms led by both NHS Digital and the Private Hospital Information Network. The importance of clinical governance has been recognised and we know that some important reforms have been initiated but not how well they are working, particularly to address the way clinical governance works across the interface and between organisations.

In this study, we address four main research questions:

- 1. What are the characteristics of the patient population and the care provision in NHS and independent hospitals in England, and what differences are observed by funding type (NHS or private), care setting (NHS or independent), specialty, procedure, geography and over time?
- 2. Can we map and measure the overall scope of practice of doctors providing care in both NHS and independent hospitals, and explore how well those organisations understand and oversee that scope of practice through the separate and shared arrangements for clinical governance that they have in place?
- 3. How does the quality and safety of care provided in NHS and independent hospitals differ, and what hospital, consultant, or other characteristics are associated with such variations?
- 4. How have the practice and working arrangements between NHS and independent hospitals changed during and after the COVID19 pandemic, and what effects have those changes had on clinical governance and the quality and safety of care?

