- Hospital Episode Statistics (NHS Digital): hospital data covering all NHS provided or NHS funded care. This includes private patients treated in NHS hospitals and NHS patients treated in independent hospitals (quadrants A, B and C from Diagram 1). Data cover patients admitted to hospital and A&E attendances. Data include information on patient characteristics; diagnosis and treatment codes; where the treatment is delivered; cost of treatment; the consultant responsible for each episode of care; length of stay; and how the patient was discharged. Data are of good quality, as they relate to how hospitals are funded for the care they deliver. We will use admitted patient data from 2014 to 2024 for WP1, WP4 and WP5 and A&E attendance data from 2021 to 2024 for WP5.
- Independent sector admitted patient care (PHIN): hospital data covering all admitted patient
 care that is privately funded (quadrants B and D from Diagram 1). The data items collected and
 data definitions are based on those in Hospital Episode Statistics for admitted patients. Note that
 no data are collected for privately funded outpatient care. The Competition and Markets
 Authority order mandates that all providers submit admitted patient data to PHIN. We will use
 aggregated data from 2017 to 2024 for WP1 and WP4.
- Patient-reported outcome measures (PROMs) for hip and knee surgery (NHS Digital): patient-level data collected using pre- and post-operative questionnaires completed by patients undergoing hip or knee replacement. All patients are invited to complete these questionnaires however their treatment is funded or provided. Patients report on changes in their health following surgery using validated condition-specific measures of self-reported health status (Oxford Hip Score and Oxford Knee Score). Aggregated PROMs data are available from PHIN

for privately funded treatment. NHS Digital will provide patient level PROMs data for NHS-funded treatment (quadrants A and C) and treatment in NHS private patient units (quadrant B). We will use data from 2022 to 2024 in WP5.

As providers of these datasets, NHS Digital and PHIN support the work and have been consulted in the planning of our research questions and work packages. PHIN have further been involved in developing the proposal. The research team has considerable experience in applying for and analysing hospital data and has long standing working relationships with NHS Digital.

Data storage

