NHS-funded hospital care (quadrants A and C in Diagram 1) is reimbursed through the national Payment by Results tariff system which incentivises detailed recording of comorbidities, but privately funded care in NHS private patient units (quadrant B) is reimbursed/charged according to the price schedules of insurers and hospitals. This may lead to differences in coding practice across sectors influencing comparisons of scope of practice (WP4) and performance (WP5). We will assess differences in the coding of comorbidities in terms of completeness and depth, across sectors and how coding changes over time. NHS funded patients in NHS hospitals vs independent hospitals offer an opportunity to compare coding in different providers but where the incentives for coding are the same. Similarly, comparing patients treated in NHS hospitals vs NHS private patient units offers an opportunity where the setting is the same but coding incentives and payments differ.

- Completeness: We will explore completeness of data fields, in terms of patient demographic characteristics (ie. age, gender, ethnicity, LSOA of residence) by quantifying the proportion of missing/unknown values for each demographic characteristic across the 3 quadrants and make comparisons between the quadrants over time.
- Depth: Diagnoses and procedures from HES are coded using International Classification of
 Diseases 10th revision (ICD-10) and OPCS-4 codes. Up to 20 diagnosis and 24 operation
 codes are recorded for each. Information in the first diagnosis position reflects the primary
 diagnosis, with subsequent positions documenting other comorbidities. Comorbidities will be
 extracted from all diagnosis and operation codes from hospital admissions between April
 2017 and February 2024. To compare coding depth, we will calculate the mean and
 standard deviation number of diagnoses codes for each patient, and calculated the mean
 number and standard deviation of diagnoses codes in each quadrant and make comparisons
 across age groups and over time.

WP2 – Survey of clinical governance leads in NHS and independent hospitals in England (RQ2, RQ3, RQ4 - lead [name])

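### Private versus NHS funding inside NHS hospitals (B vs A) holds the sector constant, not the hospital; add a within-hospital comparison before attributing differences to funding or coding incentives

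*Protocol*

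**What the plan says.** WP1, Coding practice, sets up two paired comparisons. NHS-funded patients in NHS and independent hospitals (A vs C) are "an opportunity to compare coding in different providers but where the incentives for coding are the same". For B vs A, "comparing patients treated in NHS hospitals vs NHS private patient units offers an opportunity where the setting is the same", while incentives and payments differ.

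The analyses that follow are by quadrant. Completeness is the proportion of "missing/unknown values for each demographic characteristic across the 3 quadrants and make comparisons between the quadrants over time". Depth is the mean and standard deviation of the number of "diagnoses codes in each quadrant and make comparisons" by age group and over time. The source, Hospital Episode Statistics (HES), is described under Patient datasets as "hospital data covering all NHS provided or NHS funded care".

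WP5 (Quantitative analysis of hospital data) assigns each index admission to A, B or C by funding source and type of hospital. "All regression models will include a set of indicator variables denoting the three quadrants". On how these terms are to be used, the section adds that "the associated regression coefficients will be used to test for differences in quality and safety across hospital types and funding sources". The confounders it names are demographics, area deprivation, diagnosis, comorbidities, past healthcare use and admission details such as calendar month.

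Research question 1 asks "what differences are observed by funding type (NHS or private), care setting (NHS or independent), specialty, procedure, geography and over time".

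**The concern.** Among the three quadrants analysed at patient level, B vs A is the only pair that differs in funding but not in sector. Any statement about the effect of private funding, or of different coding incentives, rests on it.

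None of the stated coding or WP5 analyses compares A and B patients inside the same hospital. The Protocol's own premises make this matter:

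- The note to Diagram 1 says that the spread of patients over quadrants varies by specialty, area and time.
- WP1 treats the provider as a source of coding differences.
- WP5 plans hospital-level estimates and funnel plots for these same indicators, so it expects hospitals to differ on them.

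An uneven mix of A and B over hospitals, combined with outcomes that vary with that mix, is enough for confounding. It does not require that some hospitals have no private patients. At stake is whether an observed A–B difference in coding, readmission, length of stay or mortality reflects how the patient was funded or which hospital treated the patient.

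**Working it through.** The Protocol gives no effect size, power or precision for this contrast, so there is no figure to reproduce. The check has four steps.

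**1. Relative size of A and B.** Diagram 1 (2020, elective acute inpatient care) gives A = 88% and B = 0.6%. B's share of care in NHS hospitals is 0.6/(88 + 0.6) = 0.68%, and A:B = 88/0.6, about 147 to 1.

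**2. Bias with no funding effect.** Let hospital h have mean outcome m_h for both funding groups, and let it supply shares a_h of A and b_h of B. The crude difference is then

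B − A = Σ (b_h − a_h) m_h.

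This is zero if a_h = b_h in every hospital, if all m_h are equal, or more generally if m_h is unrelated to the A/B mix. In the simplest case all of B lies in hospitals with mean r1, these hospitals hold a share s of A, and the rest have mean r0:

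spurious risk ratio = r1 / [s·r1 + (1 − s)·r0].

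The Protocol does not give s, r1 or r0. The readmission rates below are assumptions.

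| s | r1 (hospitals with B) | r0 (others) | A overall | Spurious ratio B/A |
|---|---|---|---|---|
| 10% | 4.5% | 6% | 0.10×4.5 + 0.90×6 = 5.85% | 4.5/5.85 = 0.77 |
| 25% | 5% | 6% | 0.25×5 + 0.75×6 = 5.75% | 5/5.75 = 0.87 |
| 50% | 5.5% | 6% | 0.50×5.5 + 0.50×6 = 5.75% | 5.5/5.75 = 0.96 |
| 100% | 5% | – | 5% | 1.00 |
| 25% | 6% | 5% | 0.25×6 + 0.75×5 = 5.25% | 6/5.25 = 1.14 |

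The last row swaps the two rates and shows that the direction can reverse. For coding depth, with an assumed difference of D = 1 code between the two kinds of hospital, the spurious difference is (1 − s)·D. That is 0.90, 0.75, 0.50, 0.25 and 0 codes for s = 10%, 25%, 50%, 75% and 100%.

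**3. Within-hospital contrast.** In the same set-up A and B patients of hospital h share the mean m_h, so the difference inside each hospital is zero and so is any weighted average of these differences.

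**4. Precision.** With equal variances the standard error is proportional to √(1/n_B + 1/n_A). Using all of A, the term relative to 1/n_B is 1 + 1/146.7 = 1.0068. Using only 10% of A it is 1 + 1/14.67 = 1.068. The ratio of standard errors is √(1.068/1.0068) = 1.03, so about 3% is lost if the A:B ratio is similar across the hospitals kept. B sets the precision in both analyses.

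**The case against.** Several points on the other side stand.

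- Research question 1 uses care setting at sector level, NHS or independent. In that sense the WP1 sentence is correct. A reader might infer that the Protocol claims to hold the individual hospital constant or to isolate a pure funding effect. It does not: it calls the comparison an opportunity, and WP5 speaks of testing for differences in average quality across quadrants. That average is a legitimate target, and research question 3 treats hospital characteristics as part of the question.
- The WP5 confounder list is open-ended, and the statistical analysis plan, which is not at hand, could add hospital terms. The absence of a hospital term is therefore not shown to be final.
- The size of any bias cannot be derived. The Protocol does not say that hospitals with private patients differ in any outcome, and the planned models adjust for case-mix and are stratified by procedure, which the illustration is not.
- A reader might infer that, because A is so large, a spurious gap would be declared a finding. That does not follow, since B limits precision.

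Two apparent safeguards do not close the gap. Adjustment for provider characteristics is stated only for the WP1 mortality case-mix model, not for coding or WP5. The instrumental-variable models use the difference in travel distance and local house prices. Neither holds the NHS hospital fixed, and if area also determines which hospital treats the patient, house price could reach the outcome through the hospital.

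Leaving the matter to an added covariate would not be enough either. Hospital effects in the three-quadrant model would largely absorb C vs A, so B vs A needs an analysis of its own.

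**Conclusion.** The concern holds in a limited form. The setting is the same only at sector level. The stated coding analyses and the named WP5 terms compare B with all of A, so hospital differences can mix with the funding contrast. The illustrative spurious risk ratios of 0.77 to 0.96 rest wholly on assumed rates and shares, and the truth could be 1.00 or above 1. The material does not show that the planned result will be biased or that the three-quadrant analysis is wrong for average differences. It supports a cheap addition that would let the study say something about funding separately from hospital.

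**What to change.** Keep the planned three-quadrant analyses for average quadrant differences and for C vs A. Then:

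1. For WP1 coding completeness and depth, add an A-plus-B comparison restricted to NHS hospitals with quadrant B admissions, stratified by HES provider code or with hospital fixed effects.
2. For each WP5 indicator with quadrant B data, add the same analysis, restricted to hospitals with quadrant B admissions for the procedure concerned. Confirm first whether the patient-reported outcome data include B, because Patient datasets and WP5 describe their coverage differently.
3. Check that the provider code places a hospital's private and NHS-funded patients together. The Protocol does not state this. If private units carry separate codes, map them to the parent hospital.
4. Base any statement about funding source or coding incentives on the within-hospital result, and reword the WP1 sentence to refer to the same sector for the unrestricted comparison.
5. Report how quadrant B is spread over hospitals, so that readers can judge the unrestricted contrast.

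The cost is one extra model per indicator (per procedure in WP5) on fields already in HES. A patients in hospitals without B no longer contribute to this contrast, and estimates may be imprecise where B is sparse for a procedure.

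### WP1 sets out to assess completeness of comorbidity coding but defines completeness on demographic fields; its comorbidity counts cannot tell under-recording in quadrant B from healthier patients

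*Protocol*

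**What the plan says.** All on this point is in the protocol.

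- **WP1, Coding practice, opening paragraph.** Tariff payment rewards detailed comorbidity recording for NHS-funded care (quadrants A and C). Private care in NHS hospitals (B) is charged on other price schedules. The protocol says this may affect the WP4 and WP5 comparisons, and states the aim: "We will assess differences in the coding of comorbidities in terms of completeness and depth, across sectors and how coding changes over time". It sets up two contrasts: A with C (same incentives, different provider) and A with B, which "offers an opportunity where the setting is the same but coding incentives and payments differ".
- **Completeness bullet.** "We will explore completeness of data fields, in terms of patient demographic characteristics", carried out "by quantifying the proportion of missing/unknown values for each demographic characteristic across the 3 quadrants". The fields named are age, gender, ethnicity and small area of residence.
- **Depth bullet.** Comorbidities are extracted from the diagnosis and operation codes. The summary is the mean "number and standard deviation of diagnoses codes in each quadrant and make comparisons" across age groups and over time.
- **WP1, Case-mix.** Comparisons include "medical characteristics (length of stay, presence and count of comorbidities"), by provider type, funding source, region and time.
- **WP5, Quantitative analysis of hospital data.** The regressions adjust for comorbidities, among other covariates. The case-mix specification draws on earlier published work and on "insights from the data quality assessment conducted in WP1".

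**The concern.** The aim and the measure concern different fields. The aim is whether comorbidities that patients have are written down equally well in each quadrant. The measure is whether demographic fields are filled in. A blank ethnicity field is visible as missing. An uncoded diabetes diagnosis is not, because it looks exactly like a patient without diabetes. Demographic missingness therefore carries no direct information about the threat that the section itself describes.

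The other WP1 measures do concern comorbidity, but they are counts of what was recorded. A lower count in B fits poorer recording, healthier patients, or both. The distinction matters for WP5. If B patients are healthier, adjusting for the recorded comorbidities is broadly the right correction. If B patients are equally ill but less fully coded, the same adjustment sets their expected rate too low and makes B look worse than it is.

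**Working it through.** **Step 1. Which planned measure responds to an unrecorded comorbidity?**

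| Measure | Responds to an omitted diagnosis? | Separates omission from better health? |
|---|---|---|
| Missing demographic fields (Completeness) | No | No |
| Mean and SD of diagnosis codes (Depth) | Yes, lower count | No |
| Presence and count of comorbidities (Case-mix) | Yes, lower prevalence | No |
| A versus B contrast | Holds setting constant | No, patient health may differ |
| Comparison across age groups | Accounts for age | No, health may differ within an age group |

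**Step 2. Size, on assumed inputs.** The protocol gives no prevalence, recording rate or readmission rate, so none of its own figures can be reproduced. Assume one condition with 30% true prevalence in both A and B, readmission of 8% with it and 4% without, recorded for 90% of affected patients in A and 70% in B. There are no false-positive codes and no true quality difference.

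- True rate in each quadrant: 0.30 × 8% + 0.70 × 4% = 5.20%.
- Recorded prevalence: A 0.30 × 0.90 = 27%; B 0.30 × 0.70 = 21%.
- Rate in A among patients without the code: (0.03 × 8% + 0.70 × 4%) / 0.73 = 4.16%.
- Expected in B, using A's rates by recorded status: 0.21 × 8% + 0.79 × 4.16% = 4.97%.
- Observed/expected in B: 5.20 / 4.97 = 1.046, about 1.05.

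**Step 3. A second situation with the same recorded data on comorbidity.** Let B be truly healthier and record as well as A does: prevalence 0.21 / 0.90 = 23.3%, recording 90%.

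- Recorded prevalence in B: again 21%.
- Observed in B: 0.233 × 8% + 0.767 × 4% = 4.93%.
- Expected in B: again 4.97%.
- Ratio: 4.93 / 4.97 = 0.99.

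Recorded presence, this condition's contribution to the code count, and demographic missingness are the same in Steps 2 and 3. The ratio is 1.05 in one and 0.99 in the other.

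**Step 4. Range.** Same formulas, with recording in A kept at 90%.

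| True prevalence | Recording in B | Expected in B | Observed in B | Ratio |
|---|---|---|---|---|
| 30% | 90% | 5.20% | 5.20% | 1.00 |
| 30% | 80% | 0.24 × 8% + 0.76 × 4.16% = 5.08% | 5.20% | 1.02 |
| 30% | 70% | 4.97% | 5.20% | 1.05 |
| 30% | 50% | 0.15 × 8% + 0.85 × 4.16% = 4.74% | 5.20% | 1.10 |
| 10% | 70% | 0.07 × 8% + 0.93 × 4.04% = 4.32% | 4.40% | 1.02 |

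In the last row, the rate in A without the code is (0.01 × 8% + 0.90 × 4%) / 0.91 = 4.04%.

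**Step 5. Would a re-recording rate separate the two situations?** Among patients already known to have the condition, the share coded again would be 90% in A and 70% in B in Step 2, and 90% in both in Step 3. It conditions on known disease, so differing prevalence drops out. This assumes that the earlier code is correct, that the condition persists, and that patients with an earlier code are recorded like other affected patients.

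**The case against.** The strongest reply is that WP1 does look at comorbidity. In Step 2 the recorded prevalence is 27% in A against 21% in B; the case-mix comparison would show this and the Depth bullet would show a lower mean count. The section names differing incentives as a threat and builds contrasts around them. This stands. A reader might infer that under-recording would go undetected, and the documents do not support that: a gap in recording would be visible, but not attributable.

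A reader might also infer that complete demographic fields would falsely reassure WP5. Nothing in the protocol says that they will be read that way, and WP5 draws on published work as well as on WP1, including the depth results.

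WP5 also adjusts for past healthcare use and plans instrumental-variable models for unobserved confounding. Either may reduce the bias. Neither is designed to detect or correct a covariate whose recording differs by quadrant.

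The Depth bullet extracts comorbidities from admissions between April 2017 and February 2024. If that means a look-back across each patient's admissions, earlier NHS coding would make up part of a shortfall in B. The text does not say so.

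Finally, a SAP not shown here could define a further measure. But the protocol has itself fixed how completeness is measured, on fields that do not match the aim, so this is more than detail left for later.

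**Conclusion.** The mismatch is certain on the text: completeness of comorbidity coding is the aim, and the Completeness bullet contains no measure of it. The remaining WP1 measures fill the gap only partly, because a lower recorded burden in B cannot be assigned to recording or to health. In the worked scenarios with poorer recording in B, the spurious observed/expected ratio for one condition runs from 1.02 to 1.10, and is 1.05 in the central case. These figures show direction and mechanism; they do not estimate the bias in this study, since every rate is assumed. The combined effect of several conditions was not computed. The change is worth making because it is cheap and bears on a threat that the authors identify themselves.

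**What to change.** 1. Keep the demographic missingness table, labelled as completeness of demographic fields.
2. Add a comorbidity-completeness measure. Among patients with a long-term condition coded at an earlier HES admission, report the proportion with it coded again at a later admission, by quadrant of the later admission (A, B, C) and by year. List the conditions in advance. The planned HES admitted-patient data (2014 to 2024) and the pseudonymised patient identifier described under WP5 are sufficient.
3. If re-recording differs by quadrant, run a WP5 sensitivity analysis that defines comorbidities from earlier HES admissions rather than from the index admission alone, and report both sets of quadrant coefficients.

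The minimum alternative is to drop completeness from the comorbidity aim and state that code counts cannot separate recording from health. That removes the inconsistency without filling the gap.

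**Cost.** One rewritten bullet, one extra table and one conditional sensitivity analysis, with no new data source beyond the HES extract for which access is to be negotiated. **Downside.** Only patients with at least two HES admissions contribute to the measure, and they may be sicker than average. HES does not cover quadrant D, so earlier private stays in independent hospitals are invisible; the look-back may be thinner for B patients, and its coverage should be reported by quadrant.
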